2.3 The self-reported combined number of days the patient spends in the ED or hospital in 30- and 60-days post discharge.⁸⁷

2.4 The Zarit Caregiver Burden Scale⁸⁸, assessed at 30- and 60-days post discharge.

2.5 The Distress Thermometer,⁸⁹ assessed 30- and 60-days post discharge.

Study Population:

This study will enroll 360 seriously ill patients in SNFs and 360 caregivers.

Patients must be English speaking, have a minimum data set of 3.0, Section GG Mobility Assessment Score of 3 or less, indicating the patient requires at least 25-50% assistance for functional mobility, be diagnosed with at least 1 serious medical illness, and have a caregiver who can be enrolled in the study.

Caregivers must be English speaking and self-report that they assist the patient at home. For patients with cognitive impairment, documentation in the medical record of a caregiver who is the patient's legally authorized representative, consent of the caregiver to participate in the study as the patient's representative is additionally required.

Phase:

N/A

Description of Sites/Facilities Enrolling Participants:	Six SNFs owned by one organization will participate in this study (none participated in the Connect-Home pilot study). Inclusion criteria for SNFs: location within 120 miles of UNC and at least 15 post-acute admissions per month. Six SNFs and six home health nurses and two alternate SNFs and two alternate home health nurses for each SNF have agreed to participate. If a study site or a home health nurse becomes unavailable to participate, the alternate SNFs and nurses will participate in Connect-Home training.
Description of Study Intervention:	Connect-Home is a two-step transitional care intervention: 1) SNF staff create an individualized Transition Plan or Care and prepare the patient and caregiver to manage the patient's illness at home; and 2) within 24 hours of SNF discharge, a Connect-Home Activation RN visits the patient's home and helps the patient and caregiver implement the written Transition Plan of Care. Both intervention steps focus on 6 key care needs to optimize patient and caregiver outcomes: 1) home safety and level of assistance; 2) advance care planning; 3) symptom management; 4) medication reconciliation; 5) function and activity; and 6) coordination of follow-up medical care.
Study Duration:	This study will be ongoing for four years.

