E.4 To assess the patient's number of hospital readmissions (acute or observational stays), 30 and 60 days after discharge from a skilled nursing facility.	E.4 Patient assessment of count of hospital readmissions, assessed 30- and 60-days post discharge.	E.4 All cause re-hospitalizations is the most widely used measure of transitional care interventions. These data will be collected to estimate the representativeness of the study sample and the generalizability of the study findings.
E.5 To assess the patient's number of emergency department visits without a	E.5 Patient assessment of the count of emergency department visits without a	E.5 ED use is a most widely used measure of transitional care interventions. These

OBJECTIVES	ENDPOINTS	JUSTIFICATION FOR ENDPOINTS
hospital stay 30 and 60 days after discharge from a skilled nursing facility.	hospital stay, assessed 30- and 60-days post discharge.	data will be collected to estimate the representativeness of the study sample and the generalizability of the study findings.
E.6 To assess caregiver-reported death of the patient 30 and 60 days after discharge from a skilled nursing facility.	E.6 Caregiver reported death of the patient, assessed 30- and 60-days post discharge.	E.6 Change in the rate of patient death is not an expected study outcome; however, these data will be used to describe the sample.

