4.3 END OF STUDY DEFINITION

The end of study will be when the study team completes the final enrolled participant's 60-day assessments, and all data (including the final home health care chart reviews) have been collected from all study subjects. If a subject is withdrawn from the study due to an early termination caused by hospitalization, SNF re-admission and/or death; end of study for these patients will occur on day of early termination.

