7.2 PARTICIPANT DISCONTINUATION/WITHDRAWAL FROM THE STUDY

Subjects have the right to discontinue their participation in the Connect-Home study for any reason without penalty. The Investigator also may discontinue subjects from the study if he feels as if it is in the best interest of the subject, or if the subject is noncompliant.

Due to the inclusion criteria requiring patient and caregiver participation, if either the patient or the caregiver withdraws or is discontinued from the study, the other subject will automatically be withdrawn.

The study team will cease data collection for an individual as soon as the subject withdraws from the study. The study team will retain data collected while the subject was participating in the Connect-Home trial.

If a patient enrolled in the study does not transfer from the SNF to home (i.e., they die in the SNF or are transferred from the SNF to the hospital or to long-term care), their data will not be analyzed, and the patient and the caregiver will be withdrawn.

If a patient is discharged from the SNF to home, and then dies prior to all data being collected, the data that was collected prior to the subject's death will be retained and included in analysis. If a patient has a reported death after discharge, only the data collected prior to the date of death will be used for data collection.

If a patient is discharged from the SNF to home, and then has a hospitalization and/or re-admission to a SNF; the patient will be withdrawn from the study by research team as they are now non-compliant for data collection. The data that was collected prior to the event will be retained and included in analysis.

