Caregiver burden is measured using the Zarit Caregiver Burden Scale. It includes 12 items on a 5-point scale. Scores range 0-48, and higher scores are associated with depression and social isolation.

This measure will be assessed at 30 and 60 days post-discharge, through telephone interview with the caregiver.

Distress Thermometer²⁸

Caregiver distress is measured using the Distress Thermometer. It includes 1 item on an 11 point scale. Scores range 0-10, with scores >4 associated with poor coping and depression.

This measure will be assessed at 30 and 60 days post-discharge, through telephone interview with the caregiver.

Number of Patient Falls with Injury and Without Injury

This assessment is self-reported by the patient; falls are defined as an "unintentional change in position resulting in a resident coming to rest on the ground or lower level."

This measure will be assessed at 30 and 60 days post discharge, through telephone interview with the patient (or with the patient's legally authorized representative, responding to survey questions as the patient's proxy in cases of patients with cognitive impairment).

MD Visit

This assessment is self-reported by the patient; it is asked in a yes/no question format.

This measure will be assessed at 30 and 60 days post discharge, through telephone interview with the patient (or with the patient's legally authorized representative, responding to survey questions as the patient's proxy in cases of patients with cognitive impairment).

Hospice Enrollment

This assessment is self-reported by the patient; it is asked in a yes/no question format.

This measure will be assessed at 30 and 60 days post discharge, through telephone interview with the patient (or with the patient's legally authorized representative, responding to survey questions as the patient's proxy in cases of patients with cognitive impairment).

Home Health Care Use

This assessment is reported by the nurses and rehabilitation therapists of the patient, as a count of the number of days in home health care.

This measure will be assessed at 30 and 60 days post discharge, through telephone interview with the nurses or rehabilitation therapists.

Hospital Readmissions

This assessment is self-reported by the patient; it is a count of hospital readmissions, either acute or observational stays after SNF discharge.

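### Section 7.2 withdraws patients at a post-discharge hospitalization or SNF readmission, yet endpoint 2.3 and E.4 count hospital days and readmissions to days 30 and 60

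*Combined protocol and SAP*

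**What the plan says.** **The withdrawal rule.** Section 7.2 provides that once a patient has gone home and is then hospitalized or readmitted to a SNF, "the patient will be withdrawn from the study by research team as they are now non-compliant for data collection". It adds: "The data that was collected prior to the event will be retained and included in analysis". Elsewhere in 7.2: "The study team will cease data collection for an individual as soon as the subject withdraws from the study". When one member of a dyad leaves, "the other subject will automatically be withdrawn". Section 4.3 withdraws no one itself, but for such cases ("If a subject is withdrawn from the study due to an early termination caused by hospitalization, SNF re-admission and/or death") it places the end of study on the day of that event.

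**The outcomes.** Secondary endpoint 2.3 is "The self-reported combined number of days the patient spends in the ED or hospital in 30- and 60-days post discharge". Exploratory endpoint E.4 is "Patient assessment of count of hospital readmissions, assessed 30- and 60-days post discharge"; section 8.1 says "it is a count of hospital readmissions, either acute or observational stays after SNF discharge". The schedule in 1.2 places hospital and ED use only at the day-30 and day-60 calls. Hypothesis 3a (9.1) and the cumulative-days model (9.4.3) rest on the same counts. Section 9.4.3 uses separate marginalized zero-inflated Poisson (MZIP) models for 2.3, and 9.4.1 rules out imputing missing outcomes.

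**The concern.** Read literally, the event that is to be counted ends the counting. A patient with no hospital stay remains and contributes a low count. A patient with a stay is removed, by a rule that acts on the outcome itself.

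Endpoint 2.3 is the only non-exploratory endpoint of Aim 3. If Connect-Home changes hospitalization, the two conditions lose different numbers and kinds of patients, and the rate ratio among those retained no longer estimates the planned effect. Later quality of life, function, burden and distress are also lost for these dyads. The joint day-30/60 model for those scales still uses any day-30 value already collected; the separate models for 2.3 give no such help at day 60.

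**Working it through.** **Plan's own figures first.** Section 9.2 assumes 22% control users with a truncated-at-zero mean of 4.0 days. Solving λ/(1−e^−λ) = 4.0 gives λ = 3.921. The excess-zero probability is 1 − 0.22/(1−e^−λ) = 0.7755 (plan 0.776), and the mean is 0.22 × 4.0 = 0.880 (plan 0.881). Both reproduce. With 30% dropout, 360 × 0.70 = 252 patients are analyzed.

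**Assumptions, because the documents are silent.**
- h, the hospitalized share of acute-care users. Section 2.2 gives 20.1% re-hospitalized and 25.9% using the ED within 90 days. Treated as non-overlapping, h = 20.1/46.0 = 0.437.
- e, the days per ED-only user: 1, with 2 as a variant.
- With h = 0.437 and e = 1, the mean hospital stay is (4.0 − 0.563)/0.437 = 7.87 days.
- SNF readmissions without a hospital stay also trigger withdrawal, but no rate is given and they are not counted.

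**Reading A: the stay is known before the day-30 call.** The share of control days kept is (1−h)e/4.
- h = 0.437: 0.563/4 = 14.1% kept, 85.9% lost (71.8% lost if e = 2). At h = 1, all are lost.
- Retained control mean: 0.22 × 0.563 = 0.124, divided by 1 − 0.22 × 0.437 = 0.904, gives 0.137 days.
- Hospitalizations halved: the true mean is 0.502, IRR 0.502/0.88 = 0.57. Observed: (0.124/0.952)/(0.124/0.904) = 0.95.
- Bias in other directions: ED-only use halved, true 0.93, observed 0.50. Half of hospitalizations turned into one-day ED visits, true 0.63, observed 1.32.

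**Reading B: the stay comes to light only at the call.** The 30-day count may survive, but patients hospitalized by day 30 have no day-60 count. Assume the same event rate in days 31-60.
- Full follow-up at day 60: mean 2 × 0.88 = 1.76; prevalence 1 − 0.78² = 39%.
- Patients losing day 60: a constant hazard from 20.1% at 90 days gives 1 − 0.799^(1/3) = 7.2% by day 30 (h = 0.072/0.22 = 0.33); h = 1 gives 22%. That is 252 × 0.072 = 18 to 252 × 0.22 = 55 patients.
- Retained control mean: 0.22(1−h)e/(1−0.22h) + 0.88. At h = 0.33, e = 2: 0.295/0.927 + 0.88 = 1.20. At h = 1: 0.88.
- Retained prevalence: 1 − 0.78²/(1−0.22h), which is 34% at h = 0.33 and 22% at h = 1.
- Hospitalizations halved throughout (h = 0.437, e = 1): true 0.57; observed (0.130+0.502)/(0.137+0.88) = 0.62.
- Halved in days 0-30 only: true (0.502+0.88)/1.76 = 0.79; observed (0.130+0.88)/1.017 = 0.99.

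**Power.** This is a rough two-group Wald test on the log mean ratio, without clustering, using the plan's means of 0.881 and 1.8 (which run opposite to hypothesis 3a) and 126 per condition. The zero-inflated Poisson variances are 3.57 and 8.85.
- Day 30: SE 0.241, power 84.2% (plan 82%).
- Day 60 with full follow-up: 98.7%.
- Day 60 under B: 84.5% at h = 0.437 (86.8% if e = 2), 82-84% at h = 0.6, 72.3% at h = 1.

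**Day-7 primaries.** At constant hazard, 1 − 0.799^(7/90) = 1.7% to 1 − 0.78^(7/30) = 5.6% are hospitalized by day 7. Upper bounds at the ends of the call windows are 2-7% by day 9 (caregiver scale) and 4-13% by day 17 (CTM-15).

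**The case against.** **Hospital stays are recorded elsewhere.** Inpatient hospitalization is a serious adverse event (8.2.2), adverse events are recorded and followed until resolution (8.2.4, 8.2.5), and dropout reasons go into the annual report (10.1.5). Section 8.1 also speaks generally of chart review. A reader might infer that these days cannot be captured at all; that is too strong. What stands is that nothing routes those records to 2.3 or E.4. The chart abstractions listed are from the SNF and home health care, and neither is assigned to hospital days.

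**The authors may have meant less.** The stated reason is non-compliance with data collection, and 4.3 is conditional, so the intent may have been patients unavailable at a call. That is possible, but 7.2 attaches withdrawal to the event itself. At minimum the wording needs to be settled.

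**Reading A may be uncommon.** Apart from the day-7 call, no contact between discharge and day 30 is described, so many stays may surface only at day 30. This stands: the 86% loss and the reversed ratios belong to reading A and should not be quoted as the expected result. Under B with a constant effect, the day-60 bias is small.

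**Power.** It is tempting to say that the claim in 9.2 of higher 60-day power is wrong. The documents do not support that. At the only value of h anchored in them, day-60 power under B is still slightly above day-30 power; the order reverses only at larger assumed h.

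**Dropout.** Nor can the 18-55 patients be read as losses on top of the plan's 30%. The documents do not say whether that figure already includes these withdrawals.

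**Conclusion.** The contradiction is textual and needs no calculation: 7.2, with 4.3, ends data collection at events that 2.3, E.4, hypothesis 3a and the cumulative-days model must count. No section exempts these outcomes or gives them another source. The rule makes missingness depend on the outcome's own value.

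The size is conditional. At h = 44% and one ED day, it runs from severe at day 30 under reading A to modest at day 60 under reading B with a constant effect. Under B, an effect confined to the first 30 days would almost vanish from the 60-day estimate. Across h = 0.33 to 1 and 1-2 ED days, reading B leaves a retained day-60 control mean of 0.88-1.20 days against 1.76 and a prevalence of 22-34% against 39%. The user prevalence and mean days come from the plan; h, the ED days and an equal event rate in days 31-60 are assumptions.

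A reader might extend the point to the primary endpoints. Few patients would be hospitalized before the day-7 call, so that extension does not hold to any important degree. The point still warrants correction before the plan is relied on, because outcomes not collected at the calls may not be recoverable.

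**What to change.** - **7.2 and 4.3:** state that a post-discharge hospitalization or SNF readmission is recorded as an outcome and does not by itself end data collection for the patient or the caregiver. The right to withdraw is unchanged.
- **Follow-up:** keep these dyads in the scheduled day-30 and day-60 calls, at least for acute-care use (2.3, E.4, E.5) and death (E.6). Continuing the other scales for willing dyads is desirable but not needed to remove the contradiction.
- **Death sentence in 7.2:** it now limits use to data collected before the date of death. Amend it so that acute-care days that occurred before death count even when reported afterwards; otherwise decedents' days remain excluded.
- **8.1:** allow the caregiver to report these factual items when the patient cannot be reached.
- **9.2 (optional):** state the day-60 retention assumed, and whether the 30% dropout includes withdrawals after hospitalization.

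**Cost:** an amendment with IRB approval, some calls that are harder to complete (fatigue is a listed risk in 2.3.1), and a small extension of proxy reporting. Section 8.1 now confines proxies to legally authorized representatives of cognitively impaired patients, although 9.4.2 already accepts caregiver answers on the CTM-15 for patients unable to respond. The calls themselves are already scheduled; the documents give no budget.

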the mean CTM-15 score) among intervention patients relative to control patients, using a two-sided test at the 5% significance level. Power for Caregiver Preparedness is similarly determined. Power for secondary outcomes at 30 days post-discharge assumes a 30% dropout rate. For the control group in Aim 3, we assumed a prevalence of 22% of patients having at least one day of acute care use and, among those patients, a truncated-at-zero mean of 4.0 days. These assumptions imply that the overall mean number of acute care use days is 0.881 and the excess zero probability is 0.776. For the intervention group, we assumed an overall mean acute care use days of 1.8 and excess zero probability 0.685. Thus, assuming 30% dropout and (optimistically) zero intraclass correlation within SNFs, the MZIP model for independent outcomes has 82% power (not shown); however, the MZIP model with empirical standard errors adjusting for possible clustering within SNFs has 71% power. If there is positive intraclass correlation, power will be lower. However, for days of acute-care use within 60 days of discharge, power is higher than for 30 days due to higher prevalence and mean number of days of acute care use.

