9.3 POPULATIONS FOR ANALYSES

An intent to treat analysis will be used in which all patients/caregivers are included in the analysis according to their treatment allocation at enrollment, regardless of whether they receive the full intervention.

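### Section 7.2 withdraws patients when they are hospitalized, yet endpoint 2.3 and E.4 count hospital use over the same 30 and 60 days

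*Combined protocol and SAP*

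**What the plan says.** Section 7.2 (Participant Discontinuation/Withdrawal) deals with a patient who goes home and is then hospitalized or readmitted to a SNF: "the patient will be withdrawn from the study by research team as they are now non-compliant for data collection". It adds: "The data that was collected prior to the event will be retained and included in analysis". Data collection stops at withdrawal. The caregiver follows, because "if either the patient or the caregiver withdraws or is discontinued from the study, the other subject will automatically be withdrawn". Section 4.3 (End of Study Definition) repeats the rule: "end of study for these patients will occur on day of early termination".

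The endpoints run over the same period. Endpoint 2.3 (section 3) is the self-reported total of ED and hospital days in the 30 and 60 days after discharge. Section 8.1 defines exploratory endpoint E.4: "it is a count of hospital readmissions, either acute or observational stays after SNF discharge". The schedule of activities (1.2) places the hospital and ED questions at the day-30 and day-60 calls only.

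On analysis, section 9.3 states: "An intent to treat analysis will be used in which all patients/caregivers are included in the analysis". Section 9.4.1 rules out imputing missing outcomes. Section 9.4.3 fits marginalized zero-inflated Poisson models to the cumulative days and mentions neither an exposure offset nor any handling of withdrawn patients. Section 9.2 expects that "for days of acute-care use within 60 days of discharge, power is higher than for 30 days due to higher prevalence".

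**The concern.** Hospitalization is part of what 2.3 measures, and it is also what ends measurement. A patient admitted on day 12 has not yet been asked about acute care, so under 7.2 that patient has no 2.3 value at either time point. A patient admitted on day 45 keeps a day-30 value and loses the day-60 value. Those who remain are the patients without a hospital stay, and their acute-care days come from ED visits alone.

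Hypothesis 3a is tested on this endpoint. Missingness is determined by the outcome, so the mixed and marginalized models in 9.4.3 cannot correct for it, and because collection stops, reanalysis cannot recover the lost days. E.4 suffers in the same way. The triggers and the endpoint overlap only in part: SNF readmission triggers withdrawal but is not counted in 2.3, and an ED-only visit is counted but does not trigger withdrawal.

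**Working it through.** **Plan's own figures.** Section 9.2 assumes that 22% of control patients have any acute care by day 30, with a zero-truncated mean of 4.0 days. Solving λ/(1 − e^−λ) = 4.0 gives λ = 3.92. The excess-zero probability is 1 − 0.22/(1 − e^−3.92) = 0.776 and the overall mean is 0.22 × 4.0 = 0.880. The plan prints 0.776 and 0.881, so its figures are reproduced, and they presume that hospital days are observed.

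**Inputs for the withdrawal effect**
- 360 patients; 22% users; 0.881 mean days (sections 1.1 and 9.2).
- 90-day rates of 25.9% ED use and 20.1% rehospitalization (section 2.2).
- Assumed: these two groups do not overlap, so the hospitalized share of users is h = 20.1/46.0 = 0.437. Range tried: 0.30 to 0.60.
- Assumed: an ED-only user has e = 1 or 2 days.
- Assumed: 30% users by day 60, or 1 − (1 − 0.46)^(2/3) = 33.7% from section 2.2 at constant hazard; 4.0 days per user at day 60.

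**Patients hospitalized**
- Day 30: 360 × 0.22 × 0.437 = 34.6 (23.8 at h = 0.30; 47.5 at h = 0.60). From the 20.1% rate at constant hazard: 1 − 0.799^(1/3) = 7.2%, or 26.
- Day 60: 360 × 0.30 × 0.437 = 47; 360 × 0.337 × 0.437 = 53. From the 20.1% rate: 13.9%, or 50.
- SNF readmissions add to these counts; the plan gives no rate for them.

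**Days they hold (control, day 30)**
- Hospitalized H = 0.22 × 0.437 = 0.096; ED-only E = 0.22 × 0.563 = 0.124.
- Days per hospitalized patient m = (0.881 − E·e)/H = 7.88 (e = 1) or 6.59 (e = 2).
- Share of all days, H·m/0.881 = 86% or 72%. Strict use of 7.2 keeps the other 14% to 28%.

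**What the incidence rate ratio (IRR) reads at day 30, strict reading.** The observed mean is E·e/(1 − H); the true mean is E·e + H·m. Let Connect-Home cut H by 30%, to 0.067 (assumed).

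| ED-only use under Connect-Home | True IRR | Observed IRR |
|---|---|---|
| Unchanged (0.124) | 0.74 (e = 1), 0.78 (e = 2) | (0.124/0.933)/(0.124/0.904) = 0.97 |
| Also falls 30% (0.087) | 0.70 | (0.087/0.933)/(0.124/0.904) = 0.68 |
| Averted stays become ED-only visits (0.124 + 0.029 = 0.153) | 0.775 (e = 1), 0.85 (e = 2) | (0.153/0.933)/(0.124/0.904) = 1.19 |

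**Section 9.2 scenario as printed** (control 0.881, intervention 1.8; true IRR 2.04). For the intervention, λ = 1.8/0.315 = 5.71 and users = 0.315 × (1 − e^−5.71) = 31.4%. With h = 0.437 and equal ED-only days in both conditions, the observed IRR is [0.314 × 0.563/(1 − 0.314 × 0.437)]/[0.22 × 0.563/(1 − 0.22 × 0.437)] = 1.50.

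**Lenient reading.** Suppose the team learns of a stay at the day-30 call, records it, and then withdraws the patient. Day 30 is intact, but anyone hospitalized by day 30 has no day-60 value. As a fraction w of those hospitalized by day 60:
- 0.22/0.30 = 73%; 0.22/0.337 = 65%.
- Using section 2.2 rates at both times: 18.6%/33.7% = 55% for any use, or 7.2%/13.9% = 52% for hospitalization.

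Day-60 days kept = 1 − w × share: from 1 − 0.73 × 0.86 = 37% to 1 − 0.52 × 0.72 = 63%.

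**The case against.** The best defence is that the hospital questions are scheduled at days 30 and 60 for everyone, and that hospitalization is a serious adverse event (8.2.2) which 8.2.5 requires to be recorded whatever its cause. The stay may therefore be on file. That stands as far as it goes, but no text carries adverse-event records into 2.3 or E.4, and the schedule conflicts with 7.2 without overriding it. The lenient reading does protect day 30. It does not protect day 60, where 9.2 expects the better power.

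Three stronger readings are tempting and are not supported:
- A reader might infer that the rule always pulls the IRR toward 1. That follows only if ED-only use is unchanged, which the plan does not assume: Hypothesis 3a concerns the ED-plus-hospital composite. The table shows no attenuation in one case and a reversal in another.
- A reader might turn the 9.2 scenario around to fit Hypothesis 3a and quote a true IRR of 0.49. As printed, the intervention has the higher mean.
- A reader might treat deaths as a second defect of similar weight. Section 7.2 has a general rule for them ("only the data collected prior to the date of death will be used for data collection"), although nothing specific to 2.3. At constant hazard the 8.1% 90-day mortality in 2.2 gives about 10 deaths by day 30 and 20 by day 60, fewer than the hospitalizations. A material distortion would need a mortality difference between conditions that no section supports; section 3 does not expect one.

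It is also fair that the 30% dropout allowance in 9.2 (108 of 360) may already include these withdrawals. The plan does not say. An allowance for numbers would in any case not repair selection on the outcome.

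**Conclusion.** The conflict in the text is certain. Sections 7.2 and 4.3 remove patients because of an event that 2.3 and E.4 count, against the inclusion of all patients promised in 9.3, and nothing restores the lost days. On the strict reading 2.3 rests mainly on ED-only use; on the lenient reading the cumulative day-60 outcome is incomplete for everyone hospitalized by day 30.

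The size is much less certain. The patient counts, the share of days lost and the 37% to 63% kept at day 60 on the lenient reading all rest on the assumed hospital share of users, ED-only days, day-60 prevalence and constant hazard. The counts are not upper bounds: a 60% hospital share gives 48 by day 30. The direction of bias cannot be stated in advance. Whatever 2.3 shows, in either direction, would be hard to interpret. This should be corrected, with the weight due to a secondary endpoint; the day-7 primary endpoints are not the subject of this point.

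**What to change.** Amend 7.2 and 4.3 so that hospitalization or SNF readmission after discharge home does not withdraw the patient or the caregiver. Collect acute-care days and vital status for these dyads at the existing day-30 and day-60 calls, from the patient, proxy or caregiver, and state in 9.4.3 that serious adverse event records supplement the reports for 2.3 and E.4.

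The cost is an IRB-approved amendment, some extra follow-up of hospitalized patients at calls already planned, and more proxy-reported answers. Reporting deaths by condition beside 2.3, or adding an analysis of days alive and out of hospital, is optional and not needed to repair this defect.
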